2.1.1.4 Calculating mean UFC

To compute the mean UFC for a patient at any particular visit, at least two individual 24hr UFC specimens are required at that visit. If there are less than two samples available then mean UFC

will be considered missing for that assessment. The derived mUFC value, calculated by Novartis, will be used for all analyses.

2.1.1.5 Study day associated with a mUFC assessment

The study day associated with a mUFC assessment at any particular visit is defined as the study day of the last UFC sample collection for that visit.

2.1.1.6 Conversion of duration in days to duration in months/years

Duration in months = $12 * (\text{Duration in days})/365.25$

Duration in years = $(\text{Duration in days})/365.25$

2.1.1.7 Calculation of proportions of responders

All enrolled patients will be included in the analysis for calculating the proportion of responders at time points up to Week 48.

For calculation of proportion of responders beyond Week 48 (e.g. a time point in extension period), the following rules will be applied to determine whether patients are included in the analysis.

1) patients who declined to enter optional extension period after completion of the core phase will always be excluded.

2) patients who discontinued prior to the data cutoff date for the Final DBL will be included up to the furthest scheduled visit they could have completed if they had not discontinued early based on data cut off and last completed based on the date of last completed schedule visit and analyses cut-off date. For example, if the last completed scheduled visit for an early discontinued patient is Week 52, and the time between data cutoff and last completed scheduled visit is 8 weeks, he/she will be included in the analyses up to Week 60.

If included in the analysis for calculating the proportion of responders at a given timepoint, patients who discontinued before this timepoint will be counted as non-responders.

Patients randomized to placebo during the RW period, will not be included in the denominator for visits at which they received placebo.

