7.1.3 Treatment period

Treatment period is divided in 4 study periods as described in [Section 4.1](#). Patients should be seen for all visits on the designated day with a visit window of ± 3 days and in a fasting state.

During study period 1 (Week 1 to 12), patients will come to the site every 2 weeks. Between visits, they may be contacted by the Investigator/designee in order to increase or decrease the study drug dose based on UFC results from previous visit.

During study period 2 (Week 13 to 24), patients will come to site every 4 weeks. Although study drug dose usually remains stable during this period, adjustment may be needed based on mUFC results and for safety.

Blood samples will be collected for all patients for sparse PK purpose throughout the core study (week 1 – 48). Pharmacokinetic blood collection for a subset of approximately 20 patients will be carried out for extensive PK assessment.

During study period 3 (Week 26 to 34), patients will either continue LCI699 open label if they are not randomized and will have visits every 4 weeks; or will be randomized to one of the 2 arms and will come to site every 2 weeks.

During study period 4 (Week 35 to 48), patients will come to site every 4 weeks.

During study periods 3 and 4, patients are also allowed to have unscheduled visits at any time if they report symptoms of hypercortisolism and have their dose adjusted accordingly.

For details of assessments, please refer to [Table 7-1](#) to [Table 7-5](#) depending on study period.

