2.7 Analysis of secondary efficacy objectives

For the objectives identified below, the definition of Baseline/Randomization assessment and the method of computing confidence intervals are specified in Section [2.1.1.2](#) and Section [2.1.1.8](#) respectively. Last observation carried forward (LOCF) method will not be used in any of these analyses. For analysis using FAS, results will be presented by LCI699 group, Placebo group, Non-randomized patients, and All patients.

2.7.1 Compare the time-to-last control of mUFC during the randomized withdrawal period between patients randomized to continued LCI699 and placebo

The results of this objective were reported in the interim CSR, and will not be repeated for the Final CSR.

2.7.2 Assess the complete, partial, and overall response rate at Week 12, Week 24, Week 48, and during the extension period

The proportion of complete responders (enrolled patients with $mUFC \leq ULN$), partial responders (enrolled patients with $mUFC > ULN$ and at least 50% reduction from baseline), and overall responders (enrolled patients with $mUFC \leq ULN$ or have at least 50% reduction from baseline) will be summarized using point estimates for every scheduled visit in the core and extension (provided [adequate follow-up](#)) at which UFC is collected. 95% 2-sided CIs for response rates will be provided for Week 48, Week 60, Week 72 and the last available assessment of the study. The FAS will be used for the analyses.

2.7.3 Assess the change in mUFC during the core and extension period of study

For the actual value and change in mUFC from baseline during the overall study period, descriptive summaries will be provided for every scheduled visit in the core and extension (provided [adequate follow-up](#)) at which UFC is collected. The FAS will be used for the analysis.

Patients randomized to placebo during the RW period, will not have their mUFC values included in the analysis for visits at which they received placebo.

2.7.4 Assess the change in cardiovascular-related metabolic parameters associated with Cushing's disease during the core and extension period of the study

The following parameters will be analyzed: glucose, HbA1c, fasting lipid profile, SBP, DBP, weight, waist circumference and BMI).

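### SAP response rates at Weeks 28 and 32 count non-randomized patients who have no UFC scheduled then, so the All-patients rate dips because of the visit schedule

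*SAP*

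**What the plan says.** SAP 2.1.1.7 sets the denominator for response rates: "All enrolled patients will be included in the analysis for calculating the proportion of responders at time points up to Week 48". Its one exclusion that acts before Week 48 is that "Patients randomized to placebo during the RW period, will not be included in the denominator for visits at which they received placebo". It counts patients who discontinued before a time point as non-responders.

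SAP 2.7.2 says that complete, partial and overall response "will be summarized using point estimates for every scheduled visit in the core and extension", limited to visits with a UFC collection. For FAS analyses, SAP 2.7 adds that "results will be presented by LCI699 group, Placebo group, Non-randomized patients, and All patients", and also that "Last observation carried forward (LOCF) method will not be used in any of these analyses". SAP 2.1.1.4 treats mUFC as missing if fewer than two specimens are available at a visit.

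The visit schedule differs by group in this period. Protocol Table 7-2 marks UFC for randomized patients at Weeks 26, 28, 30, 32 and 34. Table 7-3 marks it for non-randomized patients at Weeks 26, 30 and 34 and leaves Weeks 28 and 32 blank. Protocol 7.1.3 agrees: in Study Period 3 "patients will either continue LCI699 open label if they are not randomized and will have visits every 4 weeks".

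**The concern.** Each rule is reasonable alone. Together they put a non-randomized patient who is still on treatment into the Week 28 and Week 32 denominators with no planned urine collection that could make the patient a responder. No earlier value can be carried forward.

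A table or curve of response by visit would then show the All-patients rate falling at Week 28, recovering at Week 30 and falling again at Week 32. The Non-randomized row would read about 0% at both visits. A reader of the Final CSR could take this for a temporary loss of control in open-label patients, when it reflects only who was measured.

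The All-patients summaries of observed values in SAP 2.7.3, 2.7.4 and 2.11.4 have a related weakness. Wherever a parameter is scheduled only for randomized patients, the contributing population changes from one visit to the next.

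**Working it through.** **Inputs from the documents.** SAP 3.1 gives 132 enrolled, 50% eligible for randomization, 33 per arm and 70% response on LCI699. SAP 1.2.3 gives 1:1 allocation. The split is therefore 33 LCI699, 33 placebo and 66 non-randomized.

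**The plan's own figures.** The documents state no expected rate for Week 28 or 32. The split does reproduce: 66/0.5 = 132, and 33 per arm for 70% against 30% gives 87.3% power with a continuity-corrected two-sided test, against the stated 87%.

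**Assumptions.**
- r is the share of placebo patients back on open-label LCI699 by the visit. Protocol 4.1.3.6 and 4.1.3.7 provide for this after loss of control. The documents give no figure, so r is varied from 0 to 1.
- q is the response rate that non-randomized patients would show if measured. A range of 10% to 50% is assumed.
- End-of-treatment values mapped to Week 28 or 32 are ignored.

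**Denominator at Weeks 28 and 32.** 132 − 33(1 − r) = 99 + 33r.

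**Non-randomized row.** 0/66 = 0%.

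**Highest possible All-patients rate**, if every patient on LCI699 with a scheduled UFC responds: (33 + 33r)/(99 + 33r).
- r = 0: 33/99 = 33.3%
- r = 0.5: 49.5/115.5 = 42.9%
- r = 1: 66/132 = 50.0%

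**All-patients rate at 70% response in the LCI699 arm.**
- r = 0: 0.70 × 33/99 = 23.1/99 = 23.3%
- r = 0.3, returned patients responding at 0% or 70%: 23.1/108.9 = 21.2% or 30.03/108.9 = 27.6%
- r = 0.7, same two rates: 23.1/122.1 = 18.9% or 39.27/122.1 = 32.2%

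**Week 30 for comparison**, when non-randomized patients are measured (r = 0): (23.1 + 66q)/99.
- q = 0.1: 29.7/99 = 30.0%
- q = 0.5: 56.1/99 = 56.7%

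The dip due to the schedule alone is 66q/99, which is 6.7 percentage points at q = 0.1 and 33.3 at q = 0.5.

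**Sensitivity to the eligible share f** (r = 0). The maximum is (f/2)/(1 − f/2): 25.0% at f = 0.4 and 53.8% at f = 0.7. At 70% response these become 17.5% and 37.7%. The ratio does not depend on total enrolment, so using the 137 treated patients reported under Protocol Amendment 4 in place of 132 changes nothing.

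**LCI699 group alone.** 23.1/33 = 70% at both weeks.

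**The case against.** The strongest reply is that the SAP never says a non-randomized patient without a Week 28 value is a non-responder. SAP 2.6 has an explicit missing-as-non-responder rule for the key secondary endpoint; 2.7.2 has none for patients still on study. The limit to visits with a UFC collection could also be read group by group, in which case the Non-randomized row would not be produced at these weeks. That reading is possible, but it leaves the All-patients denominator unsettled, and 2.1.1.7 as written keeps these patients in it.

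Four stronger conclusions that a reader might draw are not supported:
- *A firm 33% ceiling.* The exclusion covers placebo patients only at visits on placebo. Those who return to open-label LCI699 re-enter both numerator and denominator, so the maximum lies between 33% and 50% under the planning split.
- *Exactly 0% for non-randomized patients, all of it artefact.* Under SAP 2.1.1.3, a Visit 777 held 7 to 21 days after Week 26 or Week 30 maps to Week 28 or 32 and could supply a value. The group also includes patients who discontinued before randomization (SAP 2.2), and 2.1.1.7 counts these as non-responders on purpose.
- *Mean mUFC would look better at these visits.* SAP 2.7.3 uses observed values. Contributors include LCI699-arm patients, selected for normal mUFC at Week 24, and also returned placebo patients who had recently lost control. The direction of any shift is unknown.
- *This is the main efficacy display.* No section says so. SAP 2.1 calls all Final CSR efficacy analyses supportive, without formal testing. The endpoint in SAP Table 1-1 names Weeks 12, 24 and 48, the extension visits and the last assessment. Confidence intervals are planned only for Weeks 48, 60, 72 and the last assessment.

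**Conclusion.** The point holds as a reporting defect at two visits. Under the written rules, non-randomized patients still on treatment are counted at Weeks 28 and 32 without a scheduled UFC, so their rate is close to zero and the All-patients rate dips for a scheduling reason. On planning figures, with 70% response on LCI699 and no placebo patient returned, the All-patients rate is 23%, although the LCI699 group itself is at 70%. With 30% to 70% of placebo patients returned, it is 19% to 32%.

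The size rests on the planned 50% eligibility, on the assumed shares returned and the response among them, and on ignoring mapped end-of-treatment values. Applying q to all 66 non-randomized patients also makes the Week 30 contrast approximate, since some of them will have discontinued. The existence of the dip does not depend on these choices, provided that some non-randomized patients would be controlled when measured.

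The affected results are descriptive and supportive. The primary, key secondary and extension results are untouched. The correction is worth making before the tables are produced, but no main conclusion of the trial turns on it.

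**What to change.** State in SAP 2.1.1.7 and 2.7.2 that at Weeks 28 and 32 no Non-randomized or All-patients response rate is reported, and that rates are given for the LCI699 group only. Say in the same place that patients in that group who discontinued earlier remain in the denominator as non-responders. A rule based only on whether a UFC was scheduled could be read as dropping them, which would undo the conservative handling in 2.1.1.7.

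In SAP 2.7.3, 2.7.4 and 2.11.4, omit the All-patients summary at any visit where the parameter is not scheduled for non-randomized patients. This should be checked parameter by parameter. For mUFC, body weight, blood pressure and the questionnaires the visits are Weeks 28 and 32; for fasting plasma glucose and HbA1c, Table 7-3 has no mark at Weeks 26, 28, 30 or 32, whereas Table 7-2 marks all four.

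The cost is a few sentences in the SAP and an edit to the table and figure shells. No new data are needed and no formal test changes.

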4.1.3.8 Complete response and primary endpoint assessment

In order for a patient to be assessed as a complete responder at Week 34, all of the following conditions must be met:

- $mUFC \leq ULN$ at Week 34
- Patient was not discontinued during the randomized withdrawal period

The primary endpoint is assessed on the basis of mUFC results at the end of the randomized withdrawal period (Week 34) for all randomized patients. The endpoint compares the complete response rate (proportion of patients with $mUFC \leq ULN$) at the end of 8 weeks of randomized withdrawal (at Week 34) between patients randomized to continued LCI699 therapy vs. placebo. Patients who are discontinued during the randomized withdrawal period are not considered complete responders.

4.1.4 Study Period 4

Study Period 4 is a single-arm, open-label therapy (Week 35 to Week 48). At the end of Week 34, all patients receive open-label LCI699 treatment. The investigator has the discretion to select the dose during this period and is advised to consider the guidelines mentioned in [Section](#)

4.1.3.7. Once the patient is on open-label LCI699, the dose may remain unchanged, increased, decreased or withheld, depending on the mUFC level, and whether or not there is an AE requiring temporary interruption of study drug. Particularly during the first few weeks of open-label LCI699 treatment (after randomized withdrawal), patients may have unscheduled visits if they report symptoms of continuing hypercortisolism, glucocorticoid withdrawal, hypocortisolism, or any adverse event.

Dose adjustments may be managed via a phone call or via an unscheduled visit at the site. Please refer to [Section 6.1.1](#) for details.

Patients continue open-label therapy until Week 48. At Week 48, patients have the option to enter an extension period or discontinue LCI699 at week 48 to conclude with an end of core study visit 4 weeks off study drug (at Week 52).

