4.1.5 Optional Extension Period

Patients who continue to receive clinical benefit, as assessed by the study investigator and who wish to enter the extension period must be re-consented at week 48. Patients who enter the extension period will do so without interruption of study drug or assessments. The optional extension period will end 16 months after all patients have completed Week 72 or have discontinued early (prior to Week 72).

Study CLCI699C2301 ends when all ongoing patients have transitioned to the long-term safety follow-up study or have been offered local alternative treatment options; this period will not exceed 16 months after all ongoing patients have completed Week 72. Patients who continue to benefit from treatment and have completed Week 72 will be offered participation in a separate long-term safety follow-up study after the database lock of the core period is completed.

If the long-term safety follow-up study is opened at site, patients should transition to the long-term safety follow-up study within 2 months from the initiation visit of the study. If this option is not available, the patient can be offered a local alternative treatment option and should transition within 2 months of the option being available at site; if no local alternative treatment option is available, the patient can stay in the study until the study end (i.e. 16 months after the last patient completes Week 72). Patients entering the long-term safety follow-up study will complete an EOT visit. For these patients, the EOS visit is not applicable, as treatment on LCI699 will not be interrupted. Patients not entering the long-term safety follow-up study will complete an EOT visit, and an EOS visit 30 days after the last dose administration.

Dose adjustments if needed after Week 72 during extension period will have to be managed via a scheduled or an unscheduled visit at the site.

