2.3.1 Patient disposition

For overall study period, counts of patients for the following items will be summarized by treatment group using FAS:

- discontinued at any time*
- Primary reason for discontinuation at any time

- discontinued at or prior to Week 12
- Primary reason for discontinuation at or prior to Week 12
- discontinued at or prior to Week 24 but after Week 12
- Primary reason for discontinuation at or prior to Week 24 but after Week 12
- discontinued prior to Week 48 but after Week 24
- Primary reason for discontinuation prior to Week 48 but after Week 24
- Completed Week 48
 - Completed Week 48 and did not enter Extension period
 - Completed Week 48 and enter Extension period
- Ongoing in Extension
- Discontinuation in the Extension
- Primary reason for discontinuation in the Extension
- Discontinued at or prior to Week 72 but after Week 48
- Discontinued prior to Week 96 but after Week 72
- Discontinued after Week 96
- Completed extension

* Patients who completed Week 48 and declined to enter optional extension period are not counted as discontinuations.

For randomized withdrawal period, counts of patients for the following items will be provided in a separate disposition summaries presented by treatment group using RAS:

- discontinued from randomized treatment before completing RW period
- primary reason for discontinuation before completing RW period
- discontinued from randomized treatment at or prior to Week 28
- primary reason for discontinuation at or prior to Week 28
- discontinued from randomized treatment at or prior to Week 30 but after Week 28
- primary reason for discontinuation at or prior to Week 30 but after Week 28
- discontinued from randomized treatment at or prior to Week 32 but after Week 30
- primary reason for discontinuation at or prior to Week 32 but after Week 30
- discontinued from randomized treatment at or prior to Week 34 but after Week 32
- primary reason for discontinuation at or prior to Week 34 but after Week 32
- Completed the RW period (Week 34)

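### After Week 48 the response-rate denominator drops completers who declined the extension, a benefit-related exclusion, so the Week 60 and Week 72 rates are probably too high and not comparable with Week 48

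*SAP*

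**What the plan says.** SAP 2.1.1.7 uses two denominators. For the core phase, "All enrolled patients will be included in the analysis for calculating the proportion of responders at time points up to Week 48". For later visits, rule 1 is that "patients who declined to enter optional extension period after completion of the core phase will always be excluded". Rule 2 keeps patients who discontinued in the denominator up to the furthest visit they could have reached by the data cutoff, and of those included, "patients who discontinued before this timepoint will be counted as non-responders".

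SAP 2.3.1 adds that "Patients who completed Week 48 and declined to enter optional extension period are not counted as discontinuations". Its disposition table splits Week 48 completers only into those who entered the extension and those who did not, and asks for no reason for non-entry.

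On who may enter, Protocol 4.1.5, repeated in SAP 1.2.5, sets two conditions: "Patients who continue to receive clinical benefit, as assessed by the study investigator and who wish to enter the extension period must be re-consented". Protocol 4.1.4 puts it more loosely: "patients have the option to enter an extension period or discontinue LCI699 at week 48".

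SAP 2.7.2 reports these rates at every visit with a UFC collection, using the FAS, and "95% 2-sided CIs for response rates will be provided for Week 48, Week 60, Week 72", as well as for the last available assessment. SAP Table 1-1 defines the rates, extension visits included, as proportions of enrolled patients. SAP 2.1 classes all efficacy analyses in the Final CSR as supportive, without formal testing.

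**The concern.** Consider two patients with the same uncontrolled mUFC. One stops for lack of effect at Week 44. Rule 2 keeps that patient in the denominator as a failure at Weeks 60 and 72. The other completes Week 48 and declines to go on. Rule 1 removes that patient from numerator and denominator. Because SAP 2.3.1 does not regard decliners as discontinuations, the non-responder rule never reaches them.

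Rule 1 itself does not mention outcome. But staying in the denominator as a continuing patient depends on entry, and entry depends on the investigator seeing benefit. Leaving the denominator is therefore plausibly associated with poor control.

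The long-term responder rates are a main efficacy result of the Final CSR. A reader who sees Weeks 48, 60 and 72 in one table, each with a confidence interval and each labelled as a proportion of enrolled patients, will take the sequence as evidence of maintained or improving control. Part of any change may come only from the denominator. The SAP specifies no all-enrolled analysis at the extension visits that would show this.

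**Working it through.** The plan states no extension response rate and no number of decliners, so there is no figure to reproduce. The check is how far the rule alone can move the rate.

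**Inputs**
- N = 137 enrolled and treated (Protocol, Amendment 4 rationale; enrolment complete).
- R = 90 controlled at Week 48: an assumption, not in the documents.
- d = 10 completers excluded as decliners, r of them controlled at Week 48: assumptions.
- Every patient's status is held fixed after Week 48, and nobody stops in the extension.
- All 137 could have reached Week 60 by the cutoff. SAP 1 has the extension run 16 months beyond the point when all patients have passed Week 72 or discontinued.

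**Formulas**
- Week 48: R/N = 90/137 = 65.7%.
- Rule 1 at Week 60: (R − r)/(N − d).
- All-enrolled row, non-entrants as non-responders: (R − r)/N.
- Rule 1 exceeds the Week 48 rate if and only if r/d < R/N. Here that means r < 10 × 0.657 = 6.57, so 6 or fewer controlled.

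**Results for d = 10**

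| Controlled non-entrants r | Rule 1 | All-enrolled row | Gap (points) |
|---|---|---|---|
| 0 | 90/127 = 70.9% | 90/137 = 65.7% | 5.2 |
| 5 | 85/127 = 66.9% | 85/137 = 62.0% | 4.9 |
| 7 | 83/127 = 65.4% | 83/137 = 60.6% | 4.8 |
| 10 | 80/127 = 63.0% | 80/137 = 58.4% | 4.6 |

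Against Week 48, the rule moves the rate by +5.2 points (70.9 − 65.7) to −2.7 points (63.0 − 65.7). Against the all-enrolled row, rule 1 is higher in every case.

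**Wider range.** Take a Week 48 rate of about 50% to 70% and d from 5 to 20, still with N = 137. The largest rise is from 96/137 = 70.1% to 96/117 = 82.1% (d = 20, none controlled), +12.0 points. The largest fall is from 68/137 = 49.6% to 48/117 = 41.0% (d = 20, all controlled), −8.6 points.

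**Offset.** Patients who stop during the extension count as non-responders. With R = 90, d = 10 and r = 0, five such losses among controlled patients give 85/127 = 66.9%, and eight give 82/127 = 64.6%, below the Week 48 rate. A flat or falling curve therefore does not show that the exclusion had no effect.

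**The case against.** The strongest reply is that the direction is not established. A reader might infer that rates from Week 60 must rise without any patient improving. The documents do not support that. A rise needs non-entrants to have been controlled less often than all enrolled patients, and neither their number nor their status is given. With 90 of 137 controlled, seven or more controlled among ten non-entrants makes the rate fall. Clinical benefit is not an mUFC threshold either: Protocol 2.2 accepts that partial responders may benefit, so uncontrolled patients can enter, and controlled patients may decline for personal reasons. All of this stands. It limits the claim to a likely bias.

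A reader might also infer that every completer who does not enter is dropped. Rule 1 says *declined*. How a completer not taken on for lack of benefit is classified is not stated. The two-way disposition split makes exclusion the natural programming, but that is an inference. The gap needs closing under either reading.

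Third, finishing the planned 48 weeks and passing up an optional period is not treatment failure, so excluding some decliners is defensible. That is a fair reason to keep rule 1 for patients who leave for unrelated reasons, but not for those who leave for lack of benefit or an adverse event.

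Fourth, some of this is already visible. Week 48 is reported on all enrolled patients, the disposition table counts non-entrants, and a rate at the last available assessment gets its own interval. But the count carries no reason or Week 48 status, and the SAP does not define the denominator for the last available assessment.

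**Conclusion.** The point holds in a limited form. After Week 48 the denominator changes through an exclusion that ignores Week 48 mUFC and reason for leaving but is tied to benefit through the entry condition. The extension rates are likely, not certainly, biased upward. They are not comparable with Week 48, and calling them proportions of enrolled patients on the FAS is inaccurate.

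With 137 enrolled, and with 90 controlled at Week 48 and 10 non-entrants assumed, rule 1 gives 63.0% to 70.9% against 65.7%, with no change in any patient. It lies 4.6 to 5.2 points above an all-enrolled rate that counts non-entrants as non-responders. Different numbers of non-entrants or a different Week 48 rate would change these figures.

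It would be wrong to read this as a threat to the trial's confirmatory conclusions. The primary and key secondary analyses are at Weeks 34 and 24, before rule 1 applies, and the extension rates carry no formal test. The plan should be corrected because these rates describe long-term efficacy.

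**What to change.** 1. Treat completers who do not enter because of lack of benefit or an adverse event as discontinued under rule 2, so that they count as non-responders up to the furthest reachable visit.
2. Keep rule 1 for other decliners. At every extension visit add a row whose denominator is all enrolled patients reachable under rule 2, with all non-entrants counted as non-responders, and give 95% CIs at Weeks 60 and 72.
3. Report the number of non-entrants by reason and by Week 48 mUFC status, and label the rule 1 rate as conditional on not having declined the extension.

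Do not instead exclude only the controlled leavers and keep the uncontrolled ones as failures. With c controlled leavers that gives (90 − c)/(137 − c), which can only fall: 85/132 = 64.4% at c = 5 and 80/127 = 63.0% at c = 10, with nobody worsening. That replaces a likely upward bias with a downward one.

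The cost is some SAP wording, a flag for reason of non-entry, a small table and one extra row. Protocol 7.1.4 already has a disposition page recording why treatment stopped. Whether it separates lack of benefit from patient choice at Week 48 should be checked before programming. The added row is conservative and will look less favourable.
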